5.1 Description of the Type/Design of Study to be Conducted and Purpose

This is a non-randomized, open-label, multicenter study, divided into multiple stages.

Chronic Myelomonocytic Leukemia and MF patients consented and enrolled with Amendment 6 or prior, who are currently on active treatment or in survival follow-up, will continue to be

followed according to the schedule of events in Amendment 6. These patients will not be reconsented under Amendment 7 or beyond.

Stage 3A (CMML):

Stage 3A is a 2-arm, non-randomized, open-label multicenter study stage in patients with CMML intended to identify clinically important responses that connote clinical benefit and potential endpoints to inform the design of a pivotal Stage 3B in patients with CMML (to be added under the auspices of a separate amendment), as well as gather data on CD123 expression on pDCs and monocytes in CMML.

Stage 3A will enroll 2 populations of patients with CMML, those with CMML-1 or CMML-2 who are refractory/resistant/intolerant to HMAs, or HU, or intensive chemotherapy; and patients with treatment naïve CMML-1 or CMML-2 with molecular features associated with a poor prognosis.

In Stage 3A, patients will be administered tagraxofusp at a dose of 12 mcg/kg as a 15-minute IV infusion once daily on Day 1 to 3 of a 21-day cycle (C1 to C4) and then on Day 1 to 3 of a 28-day cycle (C5 and beyond). The dosing period may be extended for dose delays up to Day 10 of each cycle.

Efficacy assessments will include bone marrow (aspirate and biopsy), peripheral blood (complete blood count [CBC] and differential with percent monocytes, neutrophils, neutrophil precursors, immature myeloid cells, and blasts), hepatosplenomegaly by MRI or CT, other extramedullary disease (e.g., cutaneous disease, disease-related serous effusions), symptom score analysis by the MPN-SAF TSS, cytogenetic burden, molecular response, reduced dependence on transfusion, reduced risk of infection, and survival status.

Safety will be assessed throughout the duration of the study; safety assessments will include physical examinations, vital sign measurements, ECGs, clinical laboratory evaluations, adverse event (AE) reporting (including DLTs, AEs, SAEs), and reasons for treatment discontinuation due to toxicity.

Blood samples for immunogenicity assessments will be collected for the detection of tagraxofusp reactive antibodies.

Plasmacytoid dendritic cells (pDCs) and CD123 expression will be assessed centrally on all bone marrow and peripheral blood samples by flow cytometry and immunohistochemistry prior to the start of and during treatment. Additionally, leukocyte populations will be monitored in CMML.

Exploratory assessments for CMML patients will include peripheral blood for the evaluation of cytokine IL-10, CD14+/CD16-, CYTOF (Mass cytometry), and NGS sequencing at selected sites prior to the start of and during treatment.

5.2 Data Safety Review Committee

A Data Safety Review Committee (DSRC), which will include investigators and representatives from the Sponsor, will convene periodically to review data from Stages 2 and 3A of the study. The DSRC will also convene in the event of identification of unexpected AEs, or AEs occurring at a frequency or severity not previously anticipated or following deaths on-study which are considered treatment related and/or not related to the underlying disease and sequelae.

5.3 Data Collection and Study Completion

When sufficient information is available to enable assessment of the primary endpoint and selected secondary endpoints, data collection may cease. The **Study Completion** date for the entire study will be the date beyond which study data are no longer entered into the primary database and the database is locked.

6 Study Objectives

6.1.1 Stage 3A

Objectives of Stage 3A in patients with CMML are:

- To characterize the safety profile of tagraxofusp.
- To obtain preliminary evidence of response to tagraxofusp therapy as assessed by the MDS/MPN 2015 criteria (Savona 2015), with the addition of a stable disease category, and to obtain data relative to additional clinical parameters that may be used in determination of therapeutic benefit.

The MDS/MPN 2015 criteria ([Savona 2015](#)) represent the current consensus criteria for evaluation of clinical benefit in patients with CMML, beyond those specified in the IWG-MDS criteria ([Cheson 2006](#)). Thus, as an inherent component of the design of Stage 3A, responses to treatment are assessed using the MDS/MPN 2015 criteria. The hematology community has recognized that a lack of a stable disease (SD) category in the 2015 MDS/MPN IWG criteria creates considerable uncertainty in the categorization of patients on any CMML study. Therefore, a SD category, defined as those patients not belonging to any of the defined categories in the 2015 criteria, has been added as a response category.

The purpose of Stage 3A is to evaluate the clinical benefit derived from individual components, or variations thereof, of the MDS/MPN 2015 criteria that may allow for a prospective definition of a primary efficacy endpoint, that will provide the primary evidence of efficacy for regulatory decision-making in the planned confirmatory cohort (Stage 3B; to be added under the auspices of a separate amendment).

7 Populations to be Studied

Stage 3A will include patients with CMML as follows:

- Patients with 2016 WHO-defined CMML, including those with

- CMML-1 or CMML-2 who are refractory/resistant/intolerant to HMAs, or HU, or intensive chemotherapy; and
- Treatment naïve CMML-1 or CMML-2 with molecular features associated with a poor prognosis.

7.1 Patient Selection Criteria

7.1.1 Inclusion Criteria

Patients meeting all of the following criteria may be considered for enrollment:

1. The patient is \geq 18 years old.
2. The patient has a life expectancy of $>$ 6 months.
3. The patient has an Eastern Cooperative Oncology Group (ECOG) performance status (PS) of 0-2.
4. The patient has adequate baseline organ function, including cardiac, renal, and hepatic function:
 - Left ventricular ejection fraction (LVEF) \geq institutional lower limit of normal as measured by multigated acquisition scan (MUGA) or 2-dimensional (2-D) echocardiogram (ECHO) within 28 days prior to start of therapy and no clinically significant abnormalities on a 12-lead electrocardiogram (ECG).
 - Serum creatinine \leq 1.5 mg/dL.
 - Serum albumin \geq 3.2 g/dL (or \geq 32 g/L) in the absence of receipt of IV albumin within the previous 72 hours.
 - Bilirubin \leq 1.5 mg/dL.
 - Aspartate transaminase (AST) and alanine transaminase (ALT) \leq 2.5 times the upper limit of normal (ULN).
 - Creatine phosphokinase (CPK) \leq 2.5 times the ULN.
 - Absolute neutrophil count (ANC) \geq 0.5×10^9 /L.
5. If a woman of child-bearing potential (WOCBP), the patient has a negative serum or urine pregnancy test within 1 week prior to tagraxofusp treatment (intervals shorter than 1 week are acceptable, if required by institutional guidelines).
6. The patient (either male or female) agrees to use acceptable contraceptive methods for the duration of time in the study, and to continue to use acceptable contraceptive methods for 1 week after the last tagraxofusp infusion.
7. The patient has signed informed consent prior to initiation of any study-specific procedures or treatment.
8. The patient is able to adhere to the study visit schedule and other protocol requirements, including follow-up for response assessments.

9. Patient has a 2016 WHO-defined diagnosis of CMML (persistent monocytosis $\geq 1 \times 10^9/L$ for at least 3 months, with other causes excluded, and monocytes $\geq 10\%$ of WBC in peripheral blood, no criteria and no previous history of CML, ET, PV, and acute promyelocytic leukemia; if eosinophilic, neither PDGFRA, PDGFRB, FGFR1 rearrangements nor PCM1-JAK2 translocation; $< 20\%$ blasts in peripheral blood and bone marrow aspirate; > 1 following criteria: dysplasia in > 1 myeloid lineage, acquired clonal cytogenetic or molecular abnormality in hematopoietic cells).
10. Patient has 2016 WHO-defined CMML-1 (2-4% blasts in peripheral blood and/or 5-9% blasts in bone marrow) and CMML-2 (5-19% blasts in peripheral blood and/or 10-19% blasts in bone marrow, and/or presence of Auer rods) (Arber 2016).
11. Patient is refractory/resistant/intolerant, as defined for the purposes of this study (in the absence of a standard definition for CMML) below, to HMAs, or HU, or intensive chemotherapy, including:
 - **Resistance/intolerance to HU** is defined as:
 - Uncontrolled myeloproliferation, (platelets $> 400 \times 10^9/L$ and WBC $> 10 \times 10^9/L$ after 3 months of at least 2 g/day of HU); **or**
 - Myelosuppression at a clinically relevant dose; **or**
 - Presence of unacceptable HU-related non-hematological toxicities, such as mucocutaneous manifestations, gastrointestinal symptoms, pneumonitis or fever at any dose of HU.

Conventional definition for HMA failure is defined for the purposes of this study (in the absence of a standard definition for CMML) as:

- Disease progression following at least 4 to 6 cycles of 5-azacitidine or decitabine; or
- Relapse after achieving response; or
- Intolerance to 5-azacitidine or decitabine at the prescribed dose.

OR

Patient is classified as high-risk based on the presence of morphological features, as described by the 2016 WHO prognostic system (Arber 2016), and the clinical and molecular features described in molecularly-integrated prognostic systems, such as the Groupe Français des Myélodysplasies (GFM), Mayo Molecular Model (MMM), and the CMML specific prognostic model (CPSS-Mol) (Woo 2020) and thus is not expected to benefit from HMAs.

12. Patient is ineligible for an immediate allo-SCT.

7.1.2 Exclusion Criteria

Patients meeting any of the following criteria are not eligible for enrollment in any study stage:

1. Patient has persistent clinically significant toxicities Grade ≥ 2 from previous therapies, including cytotoxic chemotherapy, targeted therapies, biological therapies, or immunotherapies, not readily controlled by supportive measures (excluding alopecia, nausea, and fatigue).
2. Patient has received treatment with any disease-related therapy, including radiation therapy within 14 days of study entry.
3. Patient has received an allo-SCT within 3 months of study entry.
4. Patient has received treatment with another investigational agent within 14 days of study entry or concurrent treatment with another investigational agent.
5. Patient has previously received treatment with tagraxofusp or has a known hypersensitivity to any components of the drug product.
6. Patient has an active malignancy and/or cancer history (excluding myeloproliferative disorders and concomitant myeloid malignancies as specified in the inclusion criteria) that can confound the assessment of the study endpoints. Patients with a past cancer history (within 2 years of entry) and/or ongoing active malignancy or substantial potential for recurrence must be discussed with the Sponsor before study entry. Patients with the following neoplastic diagnoses are eligible: non-melanoma skin cancer, carcinoma in situ (including superficial bladder cancer), cervical intraepithelial neoplasia, or organ-confined prostate cancer with no evidence of progressive disease.
7. Patient has clinically significant cardiovascular disease (e.g., uncontrolled or any New York Heart Association Class 3 or 4 congestive heart failure, uncontrolled angina, history of myocardial infarction, unstable angina, or stroke within 6 months prior to study entry, uncontrolled hypertension or clinically significant arrhythmias not controlled by medication).
8. Patient has uncontrolled, clinically significant pulmonary disease (e.g., chronic obstructive pulmonary disease, pulmonary hypertension) that, in the Investigator's opinion, would put the patient at significant risk for pulmonary complications during the study.
9. Patient has known active or suspected disease involvement of the central nervous system (CNS). If suspected due to clinical findings, CNS disease should be ruled out with relevant imaging and/or examination of cerebrospinal fluid.
10. Patient is receiving immunosuppressive therapy, with the exception of corticosteroids as specified in the inclusion criteria and tacrolimus, for treatment or prophylaxis of graft-versus-host disease (GVHD). If the patient has been on immunosuppressive treatment or prophylaxis for GVHD, the treatment(s) must have been discontinued at least 14 days prior to study drug and there must be no evidence of Grade ≥ 2 GVHD.
11. Patient has uncontrolled intercurrent illness including, but not limited to, uncontrolled infection, disseminated intravascular coagulation, or psychiatric illness that would limit compliance with study requirements.
12. Patient is pregnant or breast feeding.
13. Patient has known human immunodeficiency virus (HIV).

14. Patient has evidence of active or chronic Hepatitis B or Hepatitis C infection.
15. Patient is oxygen-dependent.
16. Patient has any medical condition that in the Investigator's opinion places the patient at an unacceptably high risk for toxicities.
17. Patient requires corticosteroid therapy at a dose of > 20 mg daily for > 7 days or has had changes to their steroid regimen within 28 days of screening.
18. Patient has 2016 WHO-defined transformation to leukemia.
19. Patient has AML M4 (French-American-British subtype; myelomonocytic). (Note: if this is suspected, the NPM1 gene must be assessed to determine eligibility).

7.2 Replacement of Patients

At the discretion of the Sponsor, additional patients may be enrolled to provide sufficient patient data for analysis after a patient prematurely withdraws from the study.

8 Treatment of Subjects

8.1 Tagraxofusp Description and Storage

Tagraxofusp Injection is a biologic fusion protein comprised of recombinant human IL-3 genetically fused to truncated DT protein. Tagraxofusp targets the IL-3R, which is overexpressed on the CSCs and bulk of various leukemias and hematopoietic malignancies relative to normal hematopoietic stem cells and other hematopoietic cells.

Tagraxofusp is prepared in liquid or lyophilized formulations; study sites may be provided with either of the following:

- Tagraxofusp Injection is a preservative-free, sterile, clear, colorless solution supplied in single-dose glass vials containing 1 mL of sterile tagraxofusp solution (1mg/vial) that should be stored in a freezer between -25°C and -15°C (-13°F and 5°F).
- Tagraxofusp for Injection (lyophilized powder), 1.0 mg is supplied in single-use, sterile, 2 mL glass vials packaged in labeled, single-vial cartons (study drug) and should be stored between 2°C and 8°C (36°F – 46°F).

Documentation stating the product's expiry date will be provided with each shipment.

8.2 Study Treatment Administration Schedule

Patients will receive 12 mcg/kg of tagraxofusp by IV infusion once daily for 3 consecutive days (or 3 doses over a period not to exceed 10 days if postponement is required to allow for toxicity resolution) of a cycle in the absence of PD or other withdrawal criteria.

A treatment cycle is 21 days in C1-4 and 28 days in C5 and beyond.

The total per-patient dose is calculated based on patient body weight in kg at baseline (C1D1). This dose will be recalculated if there is a 10% or greater change from baseline in body weight.

The first cycle of tagraxofusp must be administered in the inpatient setting, with hospitalization beginning the day of the first infusion of tagraxofusp (or a prior day) and ending approximately 24 hours after the last infusion of tagraxofusp. Subsequent cycles of tagraxofusp can be administered in the inpatient setting or in a suitable outpatient ambulatory care setting that is equipped for intensive monitoring of patients with hematopoietic malignancies undergoing treatment, per the Investigator's discretion, institutional guidelines, and capabilities. Patients will be monitored for at least 1 hour (or longer at the Investigator's discretion) following the administration of each infusion of tagraxofusp in Cycle 2 and beyond.

Patients with evidence of ongoing disease control during treatment (without evidence of clinically significant PD or intolerable toxicity) may receive repeated cycles of tagraxofusp even if an overall response, in the judgment of the Investigator, is not attained.

Refer to [Section 8.2.1](#) for details regarding required pre-medication, patient monitoring procedures, and dose modification procedures for the management of tagraxofusp-related toxicity.

8.2.1 Tagraxofusp Premedication, Dose Preparation and Administration

8.2.1.1 Premedication

Patients will receive the following premedication 60 minutes (\pm 15 minutes) before each tagraxofusp infusion:

- Acetaminophen 650 mg by mouth (PO) (or equivalent dose of paracetamol).
- Diphenhydramine 50 mg IV (or equivalent dose of another H₁-histamine antagonist).
- Methylprednisolone 50 mg IV (or an equivalent dose of another corticosteroid).
- Famotidine 20 mg IV (or an equivalent dosage of another H₂-histamine antagonist).

8.2.1.2 Tagraxofusp Dosage Preparation

Tagraxofusp is administered as a 15-minute IV infusion. Tagraxofusp is prepared for administration by the pharmacy. The total per-patient dose is calculated based on the patient's baseline body weight in kg (at baseline, C1D1) including one decimal place (mcg/kg dose \times patient weight in kg [example: 12 mcg/kg \times 70.3 kg]). (The dose will be recalculated if there is a 10% or greater change from baseline in body weight.) Additional dose preparation instructions and required supplies are described in detail within the Pharmacy Manual.

8.2.1.3 Inpatient and Outpatient Setting for Dose Administration

The first cycle of tagraxofusp must be administered in the inpatient setting, with hospitalization beginning the day of the first infusion of tagraxofusp (or a prior day) and ending approximately 24 hours after the last infusion of tagraxofusp. Subsequent cycles of tagraxofusp can be administered in the inpatient setting or in a suitable outpatient ambulatory care setting that is equipped for intensive monitoring of patients with hematopoietic malignancies undergoing

treatment, per the Investigator's discretion and institutional guidelines and capabilities. Patients will be monitored for at least 1 hour (or longer at the Investigator's discretion) following each tagraxofusp infusion in Cycle 2 and beyond.

8.2.2 Patient Monitoring Procedures During the Tagraxofusp Dosing Period

During each cycle, testing and procedures that may result in withholding of a scheduled tagraxofusp infusion, (largely based on unresolved manifestations of fluid retention and/or other relevant acute toxicities during daily dosing), include findings from clinical examination including but not limited to vital signs, and clinical laboratory parameters, detailed below, and as indicated in the applicable Schedules of Events ([Table 2](#) and [Table 3](#) for Stage 2; [Table 4](#) and [Table 5](#) for Stage 3A).

Vital Signs: Blood pressure, heart rate, respiration rate, body temperature, and pulse oximetry are to be measured during screening and during the dosing period (usually Days 1, 2, and 3) immediately prior to infusion, immediately after completion of infusion, and 30 and 60 minutes post-infusion; and at subsequent time points in each cycle as indicated in the applicable Schedules of Events ([Table 2](#) and [Table 3](#) for Stage 2; [Table 4](#) and [Table 5](#) for Stage 3A).

Diagnostic Tests:

- During the dosing period prior to tagraxofusp infusion (usually Days 1, 2, 3) and at subsequent time points in each cycle as indicated in the applicable Schedules of Events ([Table 2](#) and [Table 3](#) for Stage 2; [Table 4](#) and [Table 5](#) for Stage 3A): CBC with differential, platelets, sodium, potassium, chloride, bicarbonate, blood urea nitrogen (BUN), creatinine, glucose, total protein, albumin, calcium, phosphorus, uric acid, total bilirubin, ALT, AST, alkaline phosphatase, lactate dehydrogenase (LDH), prothrombin time (PT) or International Normalized Ratio (INR), aPTT (activated partial thromboplastin time). Additional evaluation of albumin or ALT/AST during days subsequent to treatment days may be indicated in situations where abnormalities (albumin decrease, ALT/AST increase) are noted subsequent to treatment.
- Serum albumin must be ≥ 3.2 g/dL prior to first dose of tagraxofusp in Cycle 1. During tagraxofusp dosing, serum albumin must be ≥ 3.5 g/dL. If serum albumin is reduced by ≥ 0.5 g/dL from the albumin value measured prior to tagraxofusp dosing initiation for the current cycle, withhold tagraxofusp infusion and administer 25g IV albumin. Interrupt tagraxofusp dosing until serum albumin is ≥ 3.5 g/dL AND not more than 0.5 g/dL lower than the value measured prior to dosing initiation for the current cycle.
- For temperature $\geq 38^{\circ}\text{C}$, draw blood culture $\times 2$, and collect urine for urinalysis and culture.

8.2.3 Dose Delays/Modifications and Management Procedures for Toxicities Associated with Tagraxofusp

During the dosing period for each cycle, individual tagraxofusp infusions may be delayed for up to 10 days to allow for toxicity resolution.

If dosing is resumed within a cycle, any subsequent doses in that cycle must be administered within the first 10 days of that cycle; thus, patients may receive fewer than the prescribed number of doses during a given study cycle. Tagraxofusp may be resumed after the resolution of Grade 3/4 toxicities as per [Table 1](#).

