11.10 Clinical Laboratory Tests

The following assessments should be done at the time points indicated in the applicable Schedules of Events ([Table 2](#) and [Table 3](#) for Stage 2; [Table 4](#) and [Table 5](#) for Stage 3A) and processed by the local laboratory.

- Hematology: Scheduled hematology assessments should at minimum include WBC count, differential WBC (lymphocytes, monocytes, basophils, eosinophils, and neutrophils), RBC count, hematocrit, Hb, platelet count and immature myeloid cells (including blasts + myelocytes + metamyelocytes + promyelocytes + nucleated red blood cells) (for safety assessments as well as for efficacy assessments at the end of each cycle in between bone marrow assessments).
- Serum albumin: May be a component of the serum chemistry panel. See Appendix [Section 18.3](#) for administration of albumin if serum albumin decreases to < 3.0 g/dL during treatment days or in the immediate post-treatment period.
- Serum chemistry and electrolytes: ALT, albumin, alkaline phosphatase (ALP), AST, bicarbonate, bilirubin (total, direct, and indirect), BUN, calcium, chloride, CPK, creatinine, glucose, LDH, magnesium, phosphate, potassium, sodium, total protein, and uric acid.
- Coagulation parameters: PT and/or INR and aPTT.
- Urinalysis (MF patients only): Appearance, color, pH, specific gravity, ketones, leukocytes, protein, glucose, bilirubin, urobilinogen, and occult blood.

Detailed instructions for collecting, processing, storing, and shipping the samples are provided in the Laboratory Manual.

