18.3 CLS Management Guidance

Time of Presentation	CLS Sign/Symptom	Recommended Action	Tagraxofusp Dosing Management
Prior to first dose of tagraxofusp in Cycle 1	Serum albumin < 3.2 g/dL	Administer tagraxofusp when serum albumin \geq 3.2 g/dL.	
	Serum albumin < 3.5 g/dL	Administer 25g intravenous albumin (q12h or more frequently as practical) until serum albumin is \geq 3.5 g/dL AND not more than 0.5 g/dL lower than the value measured prior to dosing initiation of the current cycle.	
During tagraxofusp dosing	Δ predose body weight that is increased by \geq 1.5 kg over the previous day's predose weight	
Administer 25g intravenous albumin (q12h or more frequently as practical), and manage fluid status as indicated clinically (e.g., generally with intravenous fluids and vasopressors if hypotensive and with diuretics if normotensive or hypertensive), until body weight increase has resolved (i.e. the increase is no longer \geq 1.5 kg greater than the previous day's predose weight).
 
Administer 25g intravenous albumin (q12h, or more frequently as practical) until serum albumin is \geq 3.5 g/dL.
	
Administer 25g intravenous albumin (q12h or more frequently as practical), and manage fluid status as indicated clinically (e.g., generally with intravenous fluids and vasopressors if hypotensive and with diuretics if normotensive or hypertensive), until body weight increase has resolved (i.e. the increase is no longer \geq 1.5 kg greater than the previous day's predose weight).
 
Administer 25g intravenous albumin (q12h, or more frequently as practical) until serum albumin is \geq 3.5 g/dL.

	Edema, fluid overload and/or hypotension	
Administer 1 mg/kg of methylprednisolone (or an equivalent) per day, until resolution of CLS sign/symptom or as indicated clinically.
 
Aggressive management of fluid status and hypotension if present, which could include intravenous fluids and/or diuretics or other blood pressure management, until resolution of CLS sign/symptom or as clinically indicated.
	
Administer 1 mg/kg of methylprednisolone (or an equivalent) per day, until resolution of CLS sign/symptom or as indicated clinically.
 
Aggressive management of fluid status and hypotension if present, which could include intravenous fluids and/or diuretics or other blood pressure management, until resolution of CLS sign/symptom or as clinically indicated.

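### The albumin hold and release rules overlap at a fall of exactly 0.5 g/dL, and five protocol places give a < 3.0 g/dL threshold for treatment days where the dosing rules act below 3.5 g/dL (minor, wording only)

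*Protocol*

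**What the plan says.** Protocol 8.2.2 sets three albumin rules around dosing:

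- Before the first dose of Cycle 1: "Serum albumin must be ≥ 3.2 g/dL prior to first dose of tagraxofusp in Cycle 1".
- An absolute floor afterwards: "During tagraxofusp dosing, serum albumin must be ≥ 3.5 g/dL".
- A relative trigger: "If serum albumin is reduced by ≥ 0.5 g/dL from the albumin value measured prior to tagraxofusp dosing initiation for the current cycle", the instruction is to "withhold tagraxofusp infusion and administer 25g IV albumin".

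The next sentence of 8.2.2 keeps dosing interrupted until albumin is at least 3.5 g/dL "AND not more than 0.5 g/dL lower than the value measured prior to dosing initiation for the current cycle". Appendix 18.3 repeats the relative part of that release condition: "not more than 0.5 g/dL lower than the value measured prior to dosing initiation of the current cycle".

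On giving albumin, the readable row of 18.3 for values under 3.5 g/dL says "Administer 25g intravenous albumin (q12h or more frequently as practical) until serum albumin is" back to at least 3.5 g/dL, with the same relative condition attached. Protocol 11.10 refers the reader to 18.3 "for administration of albumin if serum albumin decreases to < 3.0 g/dL during treatment days or in the immediate post-treatment period". Four serum chemistry footnotes carry the same threshold and the same reference: Table 2 footnote 10, Table 3 footnote 5, Table 4 footnote 8 and Table 5 footnote 5. SAP Tables 7-1 to 7-4 repeat those footnotes, because the SAP takes its flow charts from the protocol.

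Protocol 12.2 and the synopsis also use 3.0 g/dL, but for days on which treatment is withheld and the time just after treatment. Both send elements of capillary leak syndrome (CLS) to 18.3.

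**The concern.** Low albumin is one of the CLS findings listed in 8.2.3.1, and these thresholds decide whether a patient is dosed and given albumin. A hold rule should give one answer for one laboratory value. Here one value satisfies both the trigger and the release.

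The second problem lies in the schedule tables, which 8.2.2 itself names when it lists the laboratory findings that may lead to a withheld infusion. Someone who relies on the footnote alone, with an albumin of 3.0 to 3.4 g/dL on a treatment day, sees no reason to give albumin. Under 8.2.2 that patient should not be dosed, and the readable row of 18.3 calls for IV albumin.

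**Working it through.** The documents give no figure to reproduce, so the check compares the rules as inequalities. Let *b* be the pre-cycle albumin and *a* the current albumin, in g/dL. Two assumptions are needed for counting: albumin is recorded to 0.1 g/dL, and *b* lies between 3.2 and 5.0.

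**Hold and release (8.2.2, 18.3)**

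- Hold: a < 3.5, or b − a ≥ 0.5.
- Release: a ≥ 3.5, and b − a ≤ 0.5.
- Both are true only when b − a = 0.5 and a ≥ 3.5, which means b ≥ 3.5 + 0.5 = 4.0.

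On the assumed grid the overlap runs from 4.0 → 3.5 to 5.0 → 4.5, which is (5.0 − 4.0)/0.1 + 1 = 11 pairs. None has a pre-cycle value below 4.0: from 3.9, for example, a fall of 0.5 gives 3.4, which is under the floor. The 11 is a count of possible value pairs and says nothing about how often they occur.

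An example: the pre-cycle value is 4.2 and the current value 3.5, a fall of 0.7. The infusion is held and albumin given. The re-check is 3.7, a fall of 4.2 − 3.7 = 0.5. Release is met, since 3.7 ≥ 3.5 and the fall is not more than 0.5. The trigger is also met, since the fall is at least 0.5.

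**Candidate edits**

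| Edit | Pairs meeting both rules | Pairs meeting neither |
|---|---|---|
| Release when the fall is < 0.5 | 0 | 0 |
| Hold when the fall is > 0.5 | 0 | 0 |

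Each edit makes the two rules exact complements. The first is the conservative one, because a fall of exactly 0.5 stays on hold.

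**Treatment-day threshold**

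| Source | Acts when | Applies to |
|---|---|---|
| 8.2.2 | < 3.5 (no dosing) | during dosing |
| 18.3, readable row | < 3.5 (IV albumin) | during dosing |
| 11.10 and Tables 2 to 5 footnotes | < 3.0 (IV albumin, citing 18.3) | treatment days and just after treatment |
| 12.2 and synopsis | < 3.0 (IV albumin) | withheld days and just after treatment |

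Recorded values below 3.5 but not below 3.0 are 3.0, 3.1, 3.2, 3.3 and 3.4, which is five values. No value is below 3.0 without also being below 3.5. The < 3.0 treatment-day text stands in 1 + 4 = 5 protocol places, plus 4 SAP copies. Before the first dose of Cycle 1 the separate 3.2 g/dL rule applies instead.

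**The case against.** **The two sentences of 8.2.2 form a sequence.** The first starts a hold and the second says when it ends. At first detection of a 0.5 fall only the hold applies, with 25 g of albumin, and no text lets a site skip it. This stands. A reader might infer that, on first seeing such a fall, one site could dose and another hold, each with support in the protocol. The documents do not support that. The overlap matters only at a re-check landing on exactly 0.5, and there the sequence does not help: the value that ends the hold meets the trigger for it again. Any dose given there is still at or above the 3.5 g/dL floor.

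**The 3.0 and 3.5 texts can both be obeyed.** Taking the stricter satisfies both, and each < 3.0 text points to 18.3, where the stricter rule is found. This stands too. A reader might call the texts contradictory, and they are not.

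**The 3.5 floor in 8.2.2 governs dosing, not giving albumin.** In 8.2.2 the albumin infusion is tied to the fall of 0.5 or more. A reader might infer that the inconsistency over giving albumin can be shown from 8.2.2 alone. It cannot: it lies between 18.3 and the 11.10 and footnote text. The table in 18.3 is damaged in the copy available, so nothing here rests on a row that seems to be absent. It rests on the < 3.5 row, which can be read, although its time-of-presentation label is printed after it.

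**Section 12.2 also uses 3.0.** A reader might count that as a further error. It is not one, because 12.2 covers different days and defers CLS elements to 18.3.

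**Conclusion.** Both points hold, and both are minor.

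The hold and release rules overlap at a single equality, a fall of exactly 0.5 g/dL with a pre-cycle value of 4.0 or higher, and in practice only at a re-check. Which values overlap follows from the inequalities. Only the count of 11 pairs depends on the assumed recording precision and range.

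The treatment-day threshold is inconsistent for 3.0 to 3.4 g/dL between the five protocol places and the rules in 8.2.2 and 18.3. The part about giving albumin relies on the readable row of 18.3. The part about dosing relies on 8.2.2.

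No sample size, endpoint or analysis is affected. SAP section 5 records that enrollment into Stage 3A was not continued and Stage 3B was not started, so the practical value is confined to any patient still being dosed and to reuse of this text elsewhere.

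**What to change.** 1. In 8.2.2 and 18.3, change the relative part of the release condition to *less than 0.5 g/dL lower*. The cost is an occasional slightly longer hold, within the 10-day dosing window of 8.2.3.
2. In 11.10 and the serum chemistry footnotes to Tables 2, 3, 4 and 5, write *< 3.5 g/dL during dosing (see 8.2.2 and 18.3)*. Keep *< 3.0 g/dL* for the immediate post-treatment period, with a pointer to 12.2. The SAP copies follow from the protocol text.
3. Leave the 3.2 g/dL rule before the first dose of Cycle 1 unchanged, and leave 12.2 as it is.

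This is one phrase in two places and one threshold in five, plus a short note to sites if any patient is still being dosed. The clinical thresholds remain the choice of the sponsor's medical team.
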